4.0 Study Intervention(s)/Investigational Agent(s)

4.1 Description: The structural and active elements of the teleABLE intervention are described in Table 1. teleABLE is adapted from the ABLE intervention. ABLE is a tailored intervention that enables stroke survivors to overcome barriers to

Page 7 of 44

VERSION DATE: 07.21.2023

engagement in their own personally meaningful non-sedentary activities. Grounded in behavioral activation, ABLE was developed with the underlying assumptions that: 1) stroke survivors consciously or subconsciously do not return to personally meaningful activities perceived as having potential to result in discomfort or failure (experiential avoidance), and 2) successful participation in personally meaningful non-sedentary activities is motivating to engage in non-sedentary activities. Additionally, sedentary behavior interventions in similarly atrisk populations demonstrated the efficacy of activity scheduling and activity monitoring which align with the behavioral activation framework [34-36].

Table 1. teleABLE intervention elements.

Table 1. teleABLE intervention elements.				
Clinician:	Occupational therapist			
Environment:	Videoconferencing (e.g., Zoom)			
Dose:	2x/week for 6 weeks (12 sessions)			
Materials:	teleABLE workbook			
Activity Scheduling:	Plan established to complete a specific activity at a specific time.			
Activity Monitoring:	Identification of activity that occurred during waking hours.			
Self-Assessment:	Explicit identification of positive and negative outcomes of activity engagement			
Problem Solving:	Participant-generated solutions to challenges identified.			
	Clinician: Environment: Dose: Materials: Activity Scheduling: Activity Monitoring: Self-Assessment:			

The intervention process is described in Table 2. Sessions 1 and 2 are focused on providing education regarding sedentary behavior, building awareness of personal sedentary behavior patterns, and identifying non-sedentary activities that are personally meaningful. The remaining sessions include an iterative process during which stroke survivors iteratively apply a 4-step strategy (ICAN Plan) that activates engagement in these non-sedentary daily activities. Participants Identify a time when they are at risk for sitting, **C**hoose an instrumental or daily activity to complete during that time, and create a specific plan to Adapt the activity by identifying solutions to anticipated barriers, and safety concerns. Participants are instructed to carry out the plan between sessions and Notice aspects of the plan that worked well or that may require a modified plan. Participants also notice how they felt during and after completing the activity. Within the Adapt step, participants are directly prompted to consider the safety of the activity and to develop a plan to assure safety. Therapists will follow the teleABLE Safety Algorithm (included with submission) to support participant dignity and safety. The ICAN process is documented on worksheets provided in the teleABLE workbook. This process guides participants through monitoring, scheduling, problem solving, and self-assessing activity engagement. This strategy enables teleABLE to be individualized to overcome participants' specific impairment and environmental barriers to engagement in preferred nonsedentary activities.

NCT05029284

VERSION DATE: 07.21.2023

Table 2. teleABLE intervention process

Week	Session	Content	Homework
1	1	Overview:What is sedentary behavior?Modifying sedentary behavior patterns	Self-monitor 1 day
	2	 Reflection: activPAL data, self-monitoring Brainstorm non-sedentary activities Introduce ICAN Plan 	Carry out ICAN PlanSelf-monitor 1 day
2 to 6 3 to 12		 Iterative process: Self-Assessment of ICAN Plan, Modify existing ICAN Plan, or Develop new ICAN Plan 	Carry out ICAN PlanSelf-monitor 1 day

The teleABLE intervention will be delivered remotely using the University of Minnesota Health Care Component Zoom account which is HIPAA-compliant and will be accessed via their own personal device. Sessions will be delivered by a research assistant who is trained and supervised by the PI (a nationally certified and state-licensed occupational therapist). Participants will complete 2 sessions per week over 6 weeks (12 total sessions). Sessions 1 and 3 to 12 are expected to last approximately 30 minutes each. Session 2 may last up to 60 minutes. A teleABLE workbook and technology manual will be mailed to participants prior to the first intervention session.

4.2 Drug/Device Handling: N/A

4.3 Biosafety: N/A

4.4 Stem Cells: N/A

4.5 Fetal Tissue: N/A

5.0 Procedures Involved

- 5.1 Study Design: This study uses a sequential case series design to refine the intervention and study protocol based on feedback from participants and the treating therapists. Participants will complete assessments at Baseline (week 1) and 2-months (week 8), participate in 12 intervention sessions over 6 weeks (weeks 2 through 7), and complete 2 interviews (mid-intervention and week 8). Participants will also wear an activPAL activity monitor for 8 days at baseline and 2-months to assess sedentary behavior.
- 5.2 Study Procedures: Participants will be recruited through Courage Kenny Rehabilitation Institute, community-based recruitment, and Fairview Health System (see section 11.1 to 11.3). Interested potential participants will complete a screening questionnaire over the telephone (see section 8.3). Those deemed eligible will meet with study staff to review the informed consent document and have an opportunity to ask questions before deciding whether they want to consent to participate in the study. Participants who choose to provide consent

Page 9 of 44

Template Revised On: 10/28/2022

VERSION DATE: 07.21.2023

will complete eConsent (see section 21.1). After providing consent, the participant will be scheduled to complete the baseline testing session. The schedule of measures is depicted in Table 3. All study procedures, including assessments and intervention sessions, will be conducted remotely using videoconferencing (HIPAA-compliant University of Minnesota Health Care Component Zoom). The study staff administering each questionnaire will display the questions and response options on the Zoom screen. In addition, study staff may read the questions aloud if the participant prefers. The participant will provide a verbal response for all measures. All procedures will be conducted for research purposes.

Table 3: Schedule of Measures

W1	W2	W3	W4	W5	W6	W7	W8
Χ							
Χ							Х
	Χ						X X X
Χ							X
Χ							Χ
Χ							Χ
Χ							X
Χ							Χ
Χ							
Χ							
							Χ
Χ							
Χ							
Χ							
Χ							
Χ							Χ
	X X X	X	X	X	X	X	X X X X X X X X X X X X X X X X X X X

NCT05029284

VERSION DATE: 07.21.2023

Unsupervised blood pressure (3	Χ		X
min/day for 7 days)			
activPAL 8-day monitoring (10	Χ		X
min instruction, 2 min/day)			
Interview 1 (30 min)		Χ	
Interview 2 (30 min)			X

NOTE: W=Week; Study intervention is delivered during weeks 2 through 7.

Measures:

- Technology Questionnaire: This is a 12-item questionnaire that was designed based on our team's findings from a prior Zoom-based intervention for people with stroke ([name] et al., in press). Participants indicate their confidence using their device and the software, indicate their current approach to each step required to join a Zoom call, and indicate their preferences for learning new technologies. The information gleaned from this questionnaire is used by the study team to support study participants throughout remote interactions that occur throughout the study.
- EuroQoL-5D-5L: This is a valid and reliable measure of health related quality
 of life among people with stroke and other at-risk populations. Participants
 rank their function on 5 items (mobility, self-care, usual activities,
 pain/discomfort, and anxiety/depression) using a 5-point Likert-type scale.
 Participants also rate how good or bad their overall health is at the time of
 assessment using a 0 to 100 scale [37, 38].
- Activity Card Sort: This is a valid and reliable measure of activity restriction among adults with stroke and disability. We will use the electronic version of this tool during which participants view photos of 100 everyday activities and categorize activities into those they a) never did, b) do less, c) gave up, d) do now, or e) want to start since the time of their stroke. For activities that the participant indicates that they do less, gave up, or want to start, they are asked to respond to the question: "Given where we're at with COVID and the effects of your stroke, how confident would you be if you did that activity today, from 1 (not at all confident) to 10 (extremely confident)?" Participants are asked to provide a rationale for their confidence level [39].
- Acceptance and Action Questionnaire-II: This is a valid and reliable measure
 of experiential avoidance among adults. Participants rank 7 statements
 regarding their emotions and worry on a 7-point Likert-type scale. Scores are
 summed, with high scores indicating high experiential avoidance [40].
- Survey of Activities and Fear of Falling in the Elderly: This is a valid and reliable questionnaire that assesses participation in 11 daily activities, and the degree to which fear related to falling is the reason for restricted participation. For each activity, participants identify: a) if they currently do the activity (yes/no), b) fear that they might fall while doing the activity using a 4-point Likert-type scale, c) reasons besides falling for avoiding or not doing the

VERSION DATE: 07.21.2023

activity, and d) amount of performance of the activity relative to 5 years ago. Scores are reported as participation restriction, mean fear scores, and can be used to classify participants based on fear of falling and activity restriction [41, 42].

- Social Problem-Solving Inventory-Revised Short Form: This is a brief measure of problem-solving approaches that has been validated against longer versions of the Social Problem-Solving Inventory. Participants will respond to 25 statements describing their approach to solving daily problems on a 0 (not at all true of me) to 4 (extremely true of me) Likert-type scale. A composite problem-solving score is derived by reverse scoring negative problem-solving domains (negative problem orientation, impulsive/careless style, avoidance style) and summing all scores. High scores (out of a possible 40) represent greater problem-solving abilities [43].
- **General Self Efficacy Scale:** This is a valid and reliable measure of self-efficacy for navigating daily life situations. Participants rate 10 statements using a 1 (not at all true) to 4 (extremely true) Likert-type scale. Scores are summed, and high scores indicate high self-efficacy [44].
- Client Satisfaction Questionnaire-8: This is a valid and reliable measure of client satisfaction with the treatment received. Participants rate 8 statements on a 1 to 4-point Likert-type scale. High scores indicate high satisfaction [45].
- Demographic Interview: These characteristics will be obtained during
 participant interview. We will obtain the following: sex, gender identity, age,
 race/ethnicity, education, employment status, occupation, presence/absence
 of support person, living situation (e.g., alone, with or without support
 person)
- Stroke History Interview: These characteristics will be obtained during participant interview. Participants will report the date, type (ischemic vs. hemorrhagic), and side of their stroke, the types of healthcare services that they received after their stroke, and whether their current activity level is higher, lower, or the same relative to pre-stroke levels.
- Self-Administered Comorbidity Questionnaire: This is a valid and reliable measure of comorbidities. Participants will indicate the presence or absence of 14 common chronic conditions (yes/no). For each condition present, participants will indicate if they are currently receiving treatment for the condition (yes/no), and if the condition limits their daily life activities (yes/no). One point is assigned to each affirmative response. The severity score is computed by summing all responses (possible scores 0 to 42). High scores indicate high comorbidity severity [46].
- Neuro-QoL Item Bank Short Forms: Upper Extremity Function (Fine Motor, ADL), Lower Extremity Function (Mobility), Cognition Function, Communication, Depression, and Anxiety will be assessed via self-report questionnaire. Each domain is measured using a short form where

VERSION DATE: 07.21.2023

participants rank their function on 5 to 8 items using a 5-point Likert-Type scale. Scores are summed and converted to T-scores which are interpreted relative to the general population (M=50, SD=10). The Neuro-QOL short forms are valid and reliable measures of the identified constructs in people with stroke [47].

- **5-Times Sit-to-Stand Test:** During this performance-based test of lower extremity strength, participants will be instructed to begin from a seated position in a chair without wheels. They will then be instructed to stand up and sit down 5 times as quickly as possible. The length of time that it takes to complete 5 sit-to-stands will be recorded. This is a valid and reliable measure of lower extremity strength among people with stroke [48].
- **30-Second Sit-to-Stand Test:** During this performance-based test of lower extremity strength, participants will be instructed to begin from a seated position in a chair without wheels. They will then be instructed to stand up and sit down as many times as they can within 30 seconds. The count of full sit-to-stand cycles will be recorded. This is a valid and reliable measure of lower body strength among community-dwelling older adults [49].
- Montreal Cognitive Assessment (MoCA): The 5-minute MoCA protocol is a
 valid and reliable screening tool for assessment of vascular cognitive
 impairment that was developed to be administered via teleconferencing. This
 is a performance-based measure where participants complete 5-word
 learning, verbal fluency, orientation to time and place, and 5-word recall
 tasks. Each item is scored by the assessor and summed (possible range 0 to
 30, low scores indicate greater impairments) [50].
- **Dyadic Adjustment Scale-7:** This is a valid and reliable measure of interpersonal relationships that has been used to assess caregiver-care recipient relationships in stroke. This questionnaire contains 7 items rated on a 6-level ordinal scale describing the extent of agreement or disagreement, frequency of interactions, and happiness in relationships [51-53].
- Inclusion of Other in Self Scale: This is a valid and reliable 2-item measure that describes the closeness of interpersonal relationships. Participants select one of 7 images which best represent their relationship with their support person and, separately, their community [54].
- Supervised Blood Pressure: Blood pressure measurements will be taken during the remote assessment session following best practices recommended by the American Heart Association and procedures in previously published trials [55, 56]. Prior to the session, participants will receive an Omron Series 5 Upper Arm blood pressure monitor in the study package that will be mailed. Participants will be instructed to abstain from caffeine, nicotine, alcohol, and food for 1 hour prior to the assessment session. During the session, the assessor will verify abstentions. If the abstentions were not followed prior to the session, the assessor will ask the participant to abstain from caffeine,

NCT05029284

VERSION DATE: 07.21.2023

nicotine, alcohol, and food for the next hour and proceed with the remaining assessments. They will then complete the supervised blood pressure measure after at least one hour has passed. Participants will be instructed in proper use the Omron Upper Arm blood pressure monitor. They will complete a 5-minute rest, followed by 3 blood pressure measurements with a 1-minute rest between each measure. In addition to documenting the systolic and diastolic blood pressure readings, the arm that was used to take the reading (left/right), most recent time any blood pressure medication was taken, and type and dose of blood pressure medication will be documented.

- Unsupervised Blood Pressure: During the same time period during which participants are wearing the activPAL monitor, they will be asked to document their morning blood pressure reading following a procedure based on the American Heart Association guidelines for self-measured blood pressure monitoring [55]. Participants will use the Omron Upper Arm blood pressure monitor that they received in the mail. During the Baseline (week 1) assessment session, they will be instructed in proper use of the monitor. Participants will be asked to take 1 blood pressure reading when they first get up in the morning. They will document each reading, the time of the reading, and if blood pressure medication was taken, the time, dose, and type of medication in the Daily Diary.
- activPAL 8-day monitoring: The activPAL micro3 (Pal Technologies, Glasgow) will be used to measure sedentary behavior. The activPAL micro3 contains a triaxial accelerometer and inclinometer which detects and records posture throughout the day (sitting/reclined/lying, standing). A validation study in people with and without stroke revealed 100% accuracy for postural detection relative to video observations [57]. We will follow a 24-hour, 8-day wear protocol that we previously deployed in preliminary studies examining post-stroke sedentary behavior [17, 58]. The device will be activated via microUSB cable, using activPAL3 Software. The device will then be waterproofed following recommendations from the manufacturer and mailed to the participant with all required materials for application. During the virtual baseline testing session, each participant will be instructed in how to adhere the device to the anterior aspect of his/her non-stroke thigh using a gentle medical-grade tape [59, 60]. With the device, participants will also receive educational information regarding the device, self-monitoring to assess for skin irritation, and steps to take should skin irritation be identified (remove the device, contact the PI). Participants will also record sleeping and non-wear time using a daily diary provided by the research team. After the monitoring period is completed, participants will return the device and daily diary to the laboratory using a pre-addressed and postage paid mailer provided by the research team. No identifying information is recorded within the device. Upon receipt of the device, raw activity monitor data will be uploaded to the study

VERSION DATE: 07.21.2023

Box folder using activPAL3 Pal Analysis Software (v.8, Pal Technologies, Glasgow) and processed using a diary-informed protocol [58, 61].

- Interview 1: This interview will be conducted within 14 days after session 5 and focus on the participants' perspectives on: 1) learning to use videoconferencing in the context of the teleABLE intervention, 2) accessing videoconferencing, and 3) ways that the therapist and/or support person support their use of videoconferencing during the study. The interview will be conducted by a research assistant supervised by the PI. We anticipate that the interview will last 30 to 60 minutes. Interviews will be audio recorded using the Zoom record function. The resulting audio file will be stored in the study's UMN BOX folder. Interviews will be transcribed by a company called Research Transcriptions (previously SameDayTranscriptions). Research Transcriptions provides confidential transcription services, using HIPAA-compliant procedures. Interviews will be transcribed in batches based on data accumulation. Deidentified transcripts will be stored in the study's UMN BOX folder.
- Interview 2: This interview will be conducted during the post-intervention assessment session after study measures are completed and will focus on participants' perspectives on the intervention, study recruitment, assessment, and intervention procedures that may enhance retention in future trials. Interviews will be audio recorded using the Zoom record function. The resulting audio file will be stored in the study's UMN BOX folder. Interviews will be transcribed by a company called Research Transcriptions (previously SameDayTranscriptions). Research Transcriptions provides confidential transcription services, using HIPAA-compliant procedures. Interviews will be transcribed in batches based on data accumulation. Deidentified transcripts will be stored in the study's UMN BOX folder.
- 5.3 Study Duration: Individual participants' study participation will occur over 8 weeks. Assessment sessions will occur during weeks 1 and 8 (2 hours per session). During the 8-day monitor wear that occurs during weeks 1 and 8, participants may spend up to 5 minutes daily completing the activPAL diary worksheet. Intervention sessions 1 and 3 through 12 will last 30 minutes each. Intervention session 2 will last 60 minutes. Interview 1, which occurs during week 5, will last 30 minutes.

We anticipate the participants will be recruited and complete all study procedures over 10 months. Data analysis will require an additional 4 months after all data are collected.

- 5.4 Use of radiation: N/A
- 5.5 Use of Center for Magnetic Resonance Research: N/A

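### Does labelling the 8-day baseline activPAL wear as week 1 put intervention days into the baseline, or leave session 2 without its data?

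*Combined protocol and SAP*

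**What the plan says.** Section 5.1 sets the measurement: "Participants will also wear an activPAL activity monitor for 8 days at baseline and 2-months to assess sedentary behavior". Section 5.3 puts it in the calendar with "During the 8-day monitor wear that occurs during weeks 1 and 8" and gives each participant eight weeks in the study.

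Section 5.2 fixes the earliest start and what follows the wear. On the start: "During the virtual baseline testing session, each participant will be instructed in how to adhere the device". On the end: "After the monitoring period is completed, participants will return the device and daily diary to the laboratory". The file is uploaded once the device has arrived. No number of days is given for the mail or the upload.

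The note to Table 3 states: "Study intervention is delivered during weeks 2 through 7". Section 4.1 plans two sessions a week for six weeks, so week 1 of Table 2 is study week 2 and holds sessions 1 and 2. In Table 2, session 1 is an overview followed by one day of self-monitoring. Session 2 has the items "Reflection: activPAL data, self-monitoring" and "Introduce ICAN Plan".

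Section 3.2 lists sedentary minutes at week 8 among the secondary outcomes, which it describes as covering feasibility and within-person behavioural change.

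**The concern.** Taken literally, the schedule has two weak points.

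First, if the wear runs into week 2 and session 1 is held before it ends, some baseline days come after the first contact with the intervention. If those days were already less sedentary, the measured within-person change would shrink towards zero. No sentence says outright that session 1 waits for the wear to finish, or that later wear days are left out of the baseline.

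Second, session 2 needs data that exist only after the wear has ended, the device has been mailed back and the file has been uploaded. If that takes longer than the days left in week 2, session 2 goes ahead without part of its planned content. The plan states neither an expected turnaround nor a fallback.

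**Working it through.** **Inputs.** Wear of 8 days, round the clock (5.2). Start no earlier than the baseline session in week 1 (5.1, 5.2). Intervention in study weeks 2 to 7 (Table 3 note), two sessions a week (4.1). Session 2 uses the activPAL data (Table 2).

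**Assumptions.** Weeks have seven days, so week 2 is days 8 to 14. Sessions 1 and 2 fall on different days of week 2, and session 2 may be as late as day 14. The first wear day is day *d*.

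**1. The plan's own label.** Counting calendar days inclusively, the last wear day is *L* = *d* + 8 − 1 = *d* + 7. For *d* = 1, *L* = 8; for *d* = 7, *L* = 14. The wear therefore always ends in week 2, and the week 1 label in 5.3 is not reproduced. On a strict count of 8 × 24 hours, *L* = *d* + 8, which is day 9 to day 15.

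**2. Weeks counted from the baseline session (*d* = 1).** *L* = 8, and 14 − 8 = 6 days remain for return and upload. If session 1 is on day 9 or later, no wear day overlaps it. If it is on day 8, the overlap is 8 − 8 + 1 = 1 wear day. On the strict count, *L* = 9, 14 − 9 = 5 days remain, and a day 8 session would touch two dates, the second only in part.

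**3. Calendar weeks, any start day in week 1.** The days left after the wear are 14 − *L* = 7 − *d*. For session 1 to follow the wear, it must fall on day *d* + 8 or later, and by day 13 so that session 2 still fits in week 2. This requires *d* ≤ 5.

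| First wear day *d* | Last wear day | Days left in week 2 | Session 1 can follow the wear, both sessions in week 2 |
|---|---|---|---|
| 1 | 8 | 6 | yes |
| 2 | 9 | 5 | yes |
| 3 | 10 | 4 | yes |
| 4 | 11 | 3 | yes |
| 5 | 12 | 2 | yes |
| 6 | 13 | 1 | no |
| 7 | 14 | 0 | no |

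**4. How exact are the week labels?** Section 5.2 allows Interview 1 up to 14 days after session 5. At two sessions a week, session 5 is in intervention week 3, which is study week 4, so the window can reach week 6. Section 5.3 simply says week 5. The labels in 5.3 are therefore nominal. The follow-up wear shows the same looseness: week 8 is days 50 to 56, so that wear ends on day 57 to 63, in week 9. No session follows it, so nothing is affected.

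**5. What order does the text imply?** Section 5.1 assigns the wear to baseline. Section 12.3 lists participants wearing the monitor for the week 1 or week 8 assessments separately from those completing intervention sessions, and gives each group its own termination procedure. Section 5.2 has morning blood pressure taken over the same period as the wear, and Table 3 gives it seven days. Seven mornings fit eight calendar dates with partial ends, which is about one week.

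**6. Where is the outcome used?** The four items analysed and benchmarked in 15.3 are intervention components, sessions attended per week, adverse events and the satisfaction score. Sedentary minutes is not among them, and no hypothesis in section 1 refers to it.

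**The case for a change.** The strongest opposing case is that reading the weeks as nominal does not supply the missing statements. No sentence ends the baseline before session 1, and no turnaround is given. On a calendar-week reading, a baseline session on day 6 or 7 cannot be followed by the full wear and then by both sessions in week 2. Sedentary minutes is a named secondary outcome, and section 7.1 offers participants their own sedentary time. The study exists to refine procedures for a later randomised trial, so a mail-return step that may not fit is something it should notice.

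Most of this stands as description. The statements are missing, and a late start is tight. It does not show that the plan fails. The order of baseline wear followed by intervention is implied in several places, and a start early in week 1 gives a clean baseline with several days for the mail. A late start can be handled by moving session 1 or 2 a few days. The benchmark of 1.5 to 2.5 sessions attended a week leaves room for modest slippage: 12 sessions over 7 weeks is 12/7 = 1.71 a week. If the data are still late, session 2 retains the participant's self-monitoring to reflect on. As for the later trial, a formative case series with interviews and weekly team meetings is suited to finding out how long the mail takes.

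**Conclusion.** The observation is correct as arithmetic, but it does not call for a change. The label in 5.3 is off by at least one day, and the turnaround before session 2 is left to the staff. With weeks counted from the baseline session and days counted inclusively, six days are available for return and upload, and at most one of eight wear days could fall on or after session 1. With calendar weeks, the time available falls from six days to none as the baseline session moves from day 1 to day 7.

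The size of any bias cannot be calculated. The documents give no effect of session 1 on sitting time, and the rules for valid days lie in a processing protocol that is cited but not reproduced. The bias is probably small, because session 1 only gives an overview and a day of self-monitoring, while the activity plan is introduced in session 2. No conclusion the plan commits to depends on it.

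This rests on reading the week labels as study phases, which the Interview 1 timing and section 12.3 support, and on staff scheduling the sessions around the wear. An analyst who finds wear days dated on or after session 1 can set them aside when computing baseline sedentary minutes, since the session dates are on record.
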